1.2 Randomization

All participants will be centrally assigned to randomized study intervention using an IRT/RTSM.

Eligible subjects will be randomly assigned to AZD4831 5 mg or matching placebo in a 1:1 ratio. Subjects will be treated with AZD4831 or placebo for 12 weeks.

1.3 Number of subjects

About 300 subjects are expected to be enrolled to achieve approximately 90 eligible subjects. Subjects will be randomly assigned at a 1:1 ratio to one of the 2 treatment groups listed below:

- AZD4831 5 mg
- Placebo matching dose

The sample size is driven by the objective to assess the efficacy of AZD4831 of lowering alanine aminotransferase (ALT). Accounting for missing data, the randomization scheme described above aims to ensure that there are at least 40 subjects exposed to AZD4831 for 12 weeks, and at least 40 subjects treated with matching placebo for 12 weeks, with evaluable observations of ALT both at baseline and at end of treatment. Under the assumption of a standard deviation of 0.50 for change from baseline in log-transformed ALT, 40 participants per arm would render 80% power to detect a 25% decrease in ALT levels at end of treatment relative to baseline for AZD4831 treated versus placebo treated on a one-sided test with an alpha of 5%. Missing observations will be imputed, but to account for a potential loss in the ability to capture treatment effect when including imputed data, the aim is to randomize 45 participants per arm.

2 CHANGES TO PROTOCOL PLANNED ANALYSES

Full analysis set have been changed to include patients who are randomized and have been given at least one dose.

Analysis on explorative endpoint *Oxidative damage biomarkers* are not included in CSR.

3 DATA ANALYSIS CONSIDERATIONS

3.1 Timing of Analyses

The study is divided into a screening period of up to 8 weeks, a planned treatment period of 12 weeks followed by a safety follow-up period of 4 weeks.

The final clinical lock for writing the CSR will occur once all subjects have completed their full study participation or withdrawn from study.

3.2 Analysis Populations

See Section [4.1.2](#) for definition of estimand populations.

3.3 General Considerations

3.3.1 General Study Level Definitions

3.3.1.1 Baseline

For Safety Analysis Set (SAS), baseline is last non-missing value prior to or on first dose date, for further details see appendix.

For analyses on the full analysis set (FAS), baseline is determined according to the same rules as for analyses on SAS, except that for subjects whose date of first dose is different from the date of randomization baseline is determined as follows:

- Baseline is defined as the last non-missing value prior to or on the date of randomization.

For both FAS & SAS, post-baseline is defined as any value after baseline value.

Further details on selecting which measurement to use as baseline value are explained in Appendix [7.1](#).

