#### **6.4 Study Intervention Compliance**

Study intervention will be administered in clinic on the day of randomization (Day 1, Visit 4), Day 29 (Visit 6), and Day 85 (Visit 8). Participants will self-administer study intervention at home on other days.

At Visit 8, a new bottle will not be dispensed at the site, and the participant will receive study intervention from the bottle they have brought from home. When participants are dosed at the site, they will receive study intervention directly from the investigator or designee, under medical supervision, after checking treatment was not taken at home before coming to the study site. The date, and time if applicable, of dose administered in the clinic will be recorded in the source documents and recorded in the eCRF. The dose of study intervention and study participant identification will be confirmed at the time of dosing by a member of the study site staff other than the person administering the study intervention.

When participants self-administer study intervention at home, compliance with study intervention will be assessed at each visit. Compliance will be assessed by direct questioning and counting returned tablets during the site visits and documented in the source documents and eCRF. Deviation(s) from the prescribed dosage regimen should be recorded in the eCRF. Participants will be provided with a dosing card to record the dose intake information (date and time) for each dose.

A record of the number of AZD4831 (mitiperstat)/placebo tablets dispensed to and taken by each participant must be maintained and reconciled with study intervention and compliance records. Intervention start and stop dates, including dates for intervention delays will also be recorded in the eCRF.

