#### **9.4.1 General Considerations**

All personnel involved with the analysis of the study will remain blinded until database lock and protocol violations have been identified and documented. Analyses will be performed by AstraZeneca or its representatives.

Nominal significance will be 5% and all tests will be one-sided. All confidence intervals will be 2-sided and 95%.

No multiplicity adjustment for alpha is planned.

For analyses both on the FAS and on the SAS, baseline is defined as the last non-missing value prior to first dose including unscheduled assessments that occurs prior to first dose.

All summary statistics will be presented in total, divided by fibrosis stage, and divided by T2DM status.

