## 9.4.2 Pharmacodynamics

### 9.4.2.1 Primary Endpoint

The primary pharmacodynamic endpoint for this study is change from baseline to Week 12 in log-transformed ALT.

The null hypothesis of no decrease in ALT comparing AZD4831 (mitiperstat) to placebo will be tested versus the alternative hypothesis of a decrease in ALT in favor of AZD4831 (mitiperstat) to placebo using a one-sided test at 5% significance level, assessed through a treatment policy estimand. The endpoint will be analyzed in a mixed effects linear model with participant as random effect, treatment, visit and treatment-by-visit interaction as fixed effects, and baseline as covariate. Data will be log-transformed before analyses, and results will be back-transformed to describe relative change versus placebo in value at end of treatment relative to baseline. Furthermore, data will also be analyzed as individual percental change, that is  $(\text{value at time } t - \text{value at baseline})/(\text{value at baseline})100\%$ , in a similar mixed effects model but without log transformation of data.

- **Treatment:** Treatment with 5 mg AZD4831 (mitiperstat) compared to placebo, administered in addition to optimal background therapy for co-morbidities
- **Population:** FAS
- **Endpoint:** Change from baseline in log-transformed ALT
- **Intercurrent events:** Intercurrent events will be ignored (treatment policy strategy) and potential missing data imputed
- **Population-level summary:** Relative change versus placebo in value at end of treatment relative to baseline

Any missing baseline ALT values will be imputed based on existing baseline values of FAS participants using PROC MI MCMC, disregarding the treatment group. For postbaseline missing ALT values, a distinction in the imputation will be made between non-monotone and monotone missing data. Monotone missing data are defined as missing data that constitute the end participant follow-up, while non-monotone missing data means that there are observations made after the missing time point. Any non-monotone missing data will be replaced using PROC MI MCMC while monotone missing data will use PROC MI regression. The imputation model will include timepoint, baseline value, and treatment group. More details will be described in the SAP.

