4.1.2 Analysis Sets

4.1.2.1 Definitions and Derivations

Full Analysis Set (FAS)

The FAS will consist of all subjects who were randomly assigned to study intervention and received at least one dose of investigational product. Subjects will be analyzed according to their randomized study medication assignment, irrespective of the treatment received.

Participants who withdraw consent to participate in the study are included up to the date of their study termination. The FAS will be considered the primary analysis set for the primary and secondary pharmacodynamics variables as well as for the exploratory pharmacodynamics variables.

Safety Analysis Set (SAS)

The SAS consists of all subjects who have received at least one dose of investigational product. Erroneously treated subjects (e.g., those randomized to treatment A but actually given treatment B) are accounted for in the treatment group of the treatment they received. A subject who has on one or several occasions received active IP is classified as active and is accounted for in the active IP treatment group. Safety Analysis Set and Safety Set can be used interchangeably.

PK Analysis Set

The PK analysis set will consist of all participants in the FAS who have received at least one dose of AZD4831 and who have at least one valid PK sample post dose.

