7.2 Imputations

For cases when baseline ALT/Pro-C3 values are missing, the (log transformed) baseline values will be imputed by the average value of (log-transformed) baseline for all non-missing. For post-baseline missing ALT/Pro-C3 values, a distinction in the imputation will be made between non-monotone and monotone missing data. Monotone missing data are defined on a subject level as missing data that constitutes the end of subject follow-up, while non-monotone missing data means that observations exist after the time point with the missing data. The steps of the imputation algorithm are described in [Table 1](#).

There are some preparations of the datasets needed prior to starting with the imputations. Each subject must have a record for all measurements indicated by the protocol; for visits where a subject did not attend or did not get a measurement, a record with the value “.” must be included into the dataset. Furthermore, indicators for last visit on treatment, and whether the subject had treatment through the whole intended treatment period of 12 weeks must also be included.

Table 1 Missing data imputation algorithm, including analysis

Step		Description
1	Impute missing baseline	For all missing (log-transformed) baseline values, impute with the average of all non-missing (log-transformed) baseline values in the FAS population.
2	Impute non-monotone missing data	Impute all non-monotone missing data using the Markov Chain Monte Carlo (MCMC) method assuming missing data are CCI [REDACTED]. This is performed using PROC MI in SAS, stratified by CCI [REDACTED], with the

		
CCI and CCI options in the MCMC statement. CCI will be generated using the seed 35273, CCI. The imputation model will include CCI assessments CCI.

3	Impute monotone missing data	
For each of the CCI imputed datasets, impute all monotone missing ALT (Pro-C3) data CCI.
 
The CCI model imputation with a CCI will be performed with the seed 99463734. The statement is CCI.
 
Subjects who had missing data CCI.
 
The CCI imputation will be conducted following a process CCI. This will involve CCI.
 
The process will utilize the seed 101010. Please note that the term CCI will need to be adjusted to reflect CCI in the dataset.

4	Analyse	Fit the pre-specified LME model with variance-covariance matrix structure set to SP(POW)(week) to each imputed

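### The SAP ties the FAS baseline to the randomization date when dosing falls on another day, contradicting the protocol's first-dose baseline and not declaring the departure

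*SAP*

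**What the plan says.** Protocol 9.4.1 gives a single rule: "For analyses both on the FAS and on the SAS, baseline is defined as the last non-missing value prior to first dose", with unscheduled assessments counted. The Amendment 1 summary of changes explains where the rule came from. It replaced a definition that also referred to randomization, and the stated reason was to align the FAS and the SAS.

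SAP 3.3.1.1 uses a first-dose anchor for the SAS. It carries the same rules over to the FAS with one exception, which applies when a participant was first dosed on a day other than the day of randomization. For those participants the SAP rule reads: "Baseline is defined as the last non-missing value prior to or on the date of randomization". The section then adds: "For both FAS & SAS, post-baseline is defined as any value after baseline value".

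Three other places matter:

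- **Use of baseline.** In Protocol 9.4.2.1 the primary model has treatment, "visit and treatment-by-visit interaction as fixed effects, and baseline as covariate". Pro-C3 is analysed in the same way, and both endpoints use the FAS.
- **FAS membership.** SAP 4.1.2.1 now requires that members also "received at least one dose of investigational product".
- **Missing baseline.** SAP 7.2, step 1, says to "impute with the average of all non-missing (log-transformed) baseline values in the FAS population".

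SAP Section 2 lists two departures from the protocol: the FAS definition and one exploratory endpoint. Baseline is not among them. The SAP amendment history records the change of baseline definition as a clarification in line with the protocol.

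**The concern.** The two documents can give the same person different baselines for the primary endpoint and for the secondary endpoint Pro-C3. Baseline enters twice, as the reference for change and as the model covariate. A person caught by the exception could also have one baseline in the FAS tables and another in the SAS tables, which is what Amendment 1 set out to prevent.

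The departure is easy to miss. Someone checking the SAP against the protocol through Section 2 or the amendment history would conclude that the baseline rule had not changed.

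**Working it through.** **The plan's own figure.** The documents attach no number to the baseline rule. The nearest figure is the sample size, and the rule does not enter it. With a 25% reduction, the log difference is -ln(0.75) = 0.2877. With SD 0.50, one-sided 5% and 80% power, n per arm = 2 × (1.645 + 0.842)² × 0.50² / 0.2877² = 37.4, so 38 (39 with the t distribution). The SAP states 40, and 40/0.90 = 44.4 gives the planned 45. The figure reproduces and stays as it is.

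**The rules side by side.** Take randomization on Day 1 and first dose k days later.

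| Case | Protocol 9.4.1 baseline | SAP 3.3.1.1 FAS baseline |
|---|---|---|
| Dose on Day 1 (as planned) | last value before dose | exception not triggered |
| Dose later, last pre-dose sample on or before Day 1 | that sample | the same sample |
| Dose later, pre-dose sample on the dosing day | that sample | last value on or before Day 1; the dosing-day sample becomes post-baseline |

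Only the third row differs. Two things must both happen: dosing moves to a later date, and the pre-dose sample is also drawn after the randomization date.

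**Where the displaced sample goes.** The SAP Table 1 window for Week 2 is Days 12 to 25.

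- k = 1 to 10 (Days 2 to 11): the sample falls in no window and enters no visit-based analysis.
- k = 11 to 24 (Days 12 to 25): it falls in the Week 2 window and could be assigned to Week 2, although taken before any drug.

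**What replaces it for ALT.** The participant's own earlier value, from a screening period of up to 8 weeks. Under the schedule footnote added by Amendment 1, Visit 3 chemistry is required only with a fresh biopsy. For historical-biopsy participants the last scheduled fallback is therefore Visit 1, though their screening may be shortened.

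**What replaces it for Pro-C3.** Protocol Table 1 shows pharmacodynamic assessment starting at Visit 4. Table 2 seems to agree, but its columns are broken in the text, so this is a reading. If there is no screening sample, the FAS baseline is missing and SAP 7.2 inserts the mean.

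**Size of the Pro-C3 effect.** With correlation rho between baseline and Week 12, replacing a person's own baseline by the mean multiplies that person's residual variance by 1/(1 - rho²). The documents give no rho, so 0.50 to 0.75 is assumed:

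- rho = 0.50: 1/(1 - 0.25) = 1.33
- rho = 0.75: 1/(1 - 0.5625) = 2.29

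The number affected is also not given. As an illustration only, suppose 5 of 90. Average residual variance then rises by a factor of about 1 + (5/90)(0.33) = 1.02 to 1 + (5/90)(1.29) = 1.07. The standard error rises by about 1% to 3.5%. With none affected, the rise is zero.

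**The case against.** The strongest reply is that the exception is coherent and almost never used. Protocol 6.4 puts the first dose on the day of randomization. The SAP's FAS study periods (3.3.1.2) also start at randomization, so a baseline fixed there fits the FAS framework and a treatment-policy estimand. This stands as far as it goes. A reader might infer that the exception serves no purpose because every FAS member now has a first dose; the documents do not support that. What remains is that the protocol chose the other rule and the SAP does not say it has departed from it.

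Three other stronger readings are tempting:

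- **That any delay in dosing discards the baseline sample.** It does not. Samples drawn on or before the randomization date are kept.
- **That the variance factor above applies to ALT.** It describes mean replacement. ALT keeps the participant's own, older value, so the factor does not measure the loss for the primary endpoint.
- **That the treatment comparison is biased.** When dosing follows randomization, both rules take a pre-treatment value in both arms. If dosing came before randomization, the SAP rule could take a post-dose value, but treatment is assigned and kits allocated through the central system, so this is remote.

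Two limits on the evidence also stand. The SAP says it serves three regional protocols, and only the version of 20 March 2023 was available. The SAP's primary-endpoint section (4.2.1) was not in the text reviewed, so endpoint-specific baseline wording there cannot be ruled out.

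**Conclusion.** The contradiction is real, is in current text and is undeclared. Its reach is small: only FAS participants dosed on a date other than randomization, and among those dosed later, only those whose pre-dose sample was drawn after the randomization date. The number is not stated and should be few if Protocol 6.4 is followed.

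For each such person a valid pre-dose sample is not used as baseline and counts as post-baseline. The cost is precision and consistency between documents and analysis sets. The sample size is unaffected. The Pro-C3 consequence rests on the reading that no screening sample is scheduled, and its size on the assumed rho and number affected.

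It is worth correcting because it concerns the reference value of the primary endpoint and the correction is cheap.

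**What to change.** 1. Delete the FAS exception in SAP 3.3.1.1 and state the Protocol 9.4.1 rule for both sets: last non-missing value before first dose, including unscheduled samples and pre-dose samples on the dosing day.
2. Amend SAP Appendix 7.1 as well. Deleting the exception alone is not enough, because the FAS would then inherit the third step of the SAS algorithm. When the only values on the dosing date are at or after the time of first dose, that step takes the first of them as baseline, ahead of any earlier pre-dose value. Remove it for ALT and Pro-C3.
3. If the sponsor prefers the randomization anchor, declare it in SAP Section 2 with a reason and correct the amendment-history entry.

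The cost is a few sentences of SAP text. A participant with no pre-dose value at all would then have a missing baseline, to be handled by the imputation rule.

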3.3.1.2 Study periods

Study periods for the full analysis set

Enrolment period

The enrolment period starts at the date of signed informed consent and ends at the date before randomization. For subjects enrolled but not randomized, the enrolment period ends on the date of last visit.

Planned treatment period

The follow-up time during the planned treatment period will be calculated from the date of randomization to the date of end of planned treatment period visit (Visit 8), irrespective of if the subject has discontinued IP prior to this visit.

If the end of the planned treatment period visit is missing or has occurred outside of the visit window, for the purpose of defining the planned treatment period, it will be replaced by the earliest of:

- the upper end of the visit window of the end of planned treatment period visit (Day 105),
- the date of withdrawal of consent,
- the date of death,
- the date of the last study visit,

where the date of death and withdrawal of consent will be considered a study visit in this context.

Full study period

The follow-up time for the full study period will be calculated from the date of randomization and to the earliest of date of death, withdrawal of consent or last study visit (the date of death and withdrawal of consent will be considered a study visit in this context).

Study periods on the safety analysis set

Pre-treatment period

The pre-treatment period starts at the date of signed informed consent and ends at the date before-first dose of IP.

On-study period

The follow-up time for the on-study period will be calculated from the date of first dose of IP and to the earliest of date of death, and withdrawal of consent. If withdrawal of consent or death did not occur, it will be calculated from the date of the first dose of IP and to the date of the last study visit.

On-treatment period

The follow-up time for the on-treatment period will be calculated from the date of first dose of IP and to the earliest of 14 days after last dose IP, date of death, and withdrawal of consent. If withdrawal of consent or death did not occur, it will be calculated from the date of first dose of IP and to the earliest of 14 days after last dose of study drug or the last study visit.

Orthostatic hypotension

Any AEs connected to orthostatic hypotension test will use date & time of first dose as start of on-study period & on-treatment period and consequently end of pre-treatment period.

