3.3.1.2 Study periods	29 Apr 2024	Changed definition of pre-treatment period to include time.	Changed so that pre-treatment period ends at timepoint of first dose instead of day before first dose.	Yes	This change is done to handle the measurements done prior to first dose on first dose day. These are to be in the pre-treatment period.
3.3.1.1 Baseline	29 Apr 2024	Changed baseline definitions.	Changed baseline definitions to be described by algorithm to be used. This takes into regard both date & time.	Yes	Clarification
3.3.1.2 Study periods	29 Apr 2024	Added special case regarding orthostatic hypotension test for study periods.	Added special case regarding orthostatic hypotension test to use time regarding on-treatment/on-study period.	Yes	Clarification

4.1.2 Analysis sets	29 Apr 2024	New set definition.	Added “All enrolled set” definition	Yes	Clarification
4.2.4.3 Handling of dropouts and missing data	29 Apr 2024	Updated to not impute exploratory data.	Updated text to “Missing data will not be imputed. There will be an assumption of missing at random for the endpoints analyzed by MMRM.”	Yes	As this is exploratory the study team decided not to impute to reduce complexity.
4.2.2.4 Primary analysis of other endpoint	29 Apr 2024	Updated to not impute exploratory data.	Changed to not impute any missing values of exploratory endpoints	Yes	As this is exploratory the study team decided not to impute to reduce complexity.
4.1.1.1 Subject disposition and completion status – definitions	29 Apr 2024	Updated with definition on screen failures	Updated with definition on screen failures	Yes	Clarification
3.3.1.1 Baseline	29 Apr 2024	Baseline algorithm description.	Moved detailed description of baseline algorithm into appendix	Yes	As it is a very detailed description defining the algorithm of picking baseline, it was moved to its own appendix.

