4.6 Safety Analyses

The domain safety covers exposure, adverse events, vital signs, ECG, and clinical laboratory.

Tables, figures, and listings are provided for SAS unless otherwise stated. All tabulations of safety data (AEs, laboratory parameters, vital signs, and ECG) will be based on both the on-treatment period and on-study period respectively unless otherwise stated.

Table 3. Overview of safety objectives

Statistical objectives	Endpoint	Population	Inter-current event strategy	Population level summary	Details in section
Primary Safety objectives					
Objective 1:					
To assess the safety and tolerability of AZD4831 as compared with placebo in participants with non-cirrhotic NASH with fibrosis.	AEs and clinical and laboratory assessments	SAS	While on treatment strategy; Treatment policy strategy	Descriptive statistics	4.6

- **Treatment** Actual treatment group (i.e., not necessarily the treatment a subject was randomized to), AZD4831 5mg or placebo administered in addition to optimal background therapy for co-morbidities
- **Population:** Safety Analysis Set
- **Endpoint:** AEs and clinical laboratory assessments
- **Intercurrent events:** Premature study treatment discontinuation: All analyses will be provided using two complementary strategies:
 - While on treatment strategy: Uses all available data collected during the on-treatment analysis period, defined in section [3.3.1.2](#)
 - Treatment policy strategy: Ignoring study treatment discontinuation, implemented by including all available data, using the on-study analysis period defined in section [3.3.1.2](#)
- **Population-level summary:** Descriptive Statistics

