4.6.3.2 Presentations

Clinical laboratory parameters will be presented for SAS by treatment group, and scheduled visit, separately for haematology and chemistry parameters, and the parameters will be presented in alphabetical order.

Values and absolute change from baseline will be presented for continuous variables using descriptive statistics for all scheduled assessments after baseline.

Maximum on-treatment/on-study ALT and AST versus maximum on-treatment/on-study total bilirubin will be presented by treatment group.

Shift tables will be presented for all subjects by treatment.

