7 APPENDIX

7.1 Baseline definitions

If there are multiple measurement on the same date, the algorithm below decides which measurement to use as baseline.

For analyses on the safety analysis set (SAS), baseline is determined as follows:

- If there is at least one non-missing value collected on the date of first dose and prior to the time of first dose, then baseline is defined as the last non-missing value prior to the time of first dose on the date of first dose.
- Else if there is at least one non-missing value collected on the date of first dose and with missing time, then baseline is defined as the non-missing value with missing time on the date of first dose.
- Else if the only values collected on the date of first dose are on or after the time of first dose, then baseline is defined as the first non-missing value on or after the time of first dose on the date of first dose.

- Else if there are no non-missing values collected on the date of first dose, then baseline is defined as the last non-missing value prior to the date of first dose.

Note: if multiple non-missing values collected on the same date qualify for baseline and include both records with missing time and records with non-missing time, then the records with missing time will not be considered as eligible to be used as baseline.

If after performing the above steps there are still multiple non-missing values equally eligible to be used as baseline, then baseline is defined as an average of the tied quantitative values or as the clinically best value among the tied qualitative values.

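### Pre-dose Day 1 laboratory samples fall inside the on-treatment and on-study periods, so they can be reported as on-treatment maxima (SAP 4.6.3.2) or as maxima and minima in the urinalysis shifts (SAP 4.6.4.1)

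*SAP*

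**What the plan says.** **Periods.** SAP 3.3.1.2 ends the pre-treatment period on the day before first dose. Both safety periods start on the date of first dose; for the on-treatment period the text is "The follow-up time for the on-treatment period will be calculated from the date of first dose of IP", and the on-study period begins in the same way. There is one exception by clock time: "Any AEs connected to orthostatic hypotension test will use date & time of first dose as start of on-study period". It does not mention laboratory data.

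**Data admitted.** SAP 4.6 bases laboratory tabulations on both periods. Its while-on-treatment strategy is described thus: "Uses all available data collected during the on-treatment analysis period".

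**Displays.** SAP 4.6.3.2 states: "Maximum on-treatment/on-study ALT and AST versus maximum on-treatment/on-study total bilirubin will be presented by treatment group". The sentence before it limits the by-visit summaries, "using descriptive statistics for all scheduled assessments after baseline", but the sentence on maxima has no such limit. SAP 4.6.4.1 plans urinalysis shift tables from baseline to the maximum and minimum on-treatment and on-study assessment, also without a limit.

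**Baseline.** If a value exists on the day of first dose before the dose, Appendix 7.1 says "then baseline is defined as the last non-missing value prior to the time of first dose on the date of first dose". SAP 3.3.1.1 adds: "For both FAS & SAS, post-baseline is defined as any value after baseline value". Neither display uses that term.

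**Timing.** The footnotes to the protocol's Schedule of Activities (1.3) have safety bloods drawn pre-dose where applicable and the Day 1 dose given at the site.

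**The concern.** Following the stated rules, a programmer would give one pre-dose sample two roles: it is the baseline, and it is a candidate for the on-treatment extreme. A value drawn before any exposure could be labelled on-treatment.

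This matters more here than in a trial that enrols people with normal liver tests. Protocol 5.1 requires raised ALT at entry and 5.2 excludes only above 5 × ULN, so a pre-dose ALT of 3 to 5 × ULN is permitted. Hepatic safety is a named part of the safety objective. If the drug lowers ALT, pre-dose values will be the maximum more often on active treatment than on placebo, which narrows the contrast between arms.

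In the urinalysis tables, including the baseline means that the maximum can never be below baseline and the minimum never above it. A shift in those directions could not appear.

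**Working it through.** **1. Where the Day 1 sample falls**

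| Question | Source | Answer for a pre-dose Day 1 blood sample |
|---|---|---|
| Pre-treatment period? | SAP 3.3.1.2 | No; it ended the day before |
| On-treatment and on-study periods? | SAP 3.3.1.2 | Yes, by date |
| Covered by the clock-time exception? | SAP 3.3.1.2 | No; orthostatic-test adverse events only |
| Baseline? | SAP 7.1, first bullet | Yes |
| Admitted to period-based analyses? | SAP 4.6 | Yes; all available data in the period |
| Excluded from the maxima? | SAP 4.6.3.2 | No |

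The laboratory row of the Schedule of Activities did not survive text extraction cleanly. That Visit 4 has a safety sample is taken from Protocol Table 1 (safety at Week 0) and the SAP visit-window table (Visit 4, target Day 1, is baseline). The pre-dose footnote concerns blood. For urine, the point applies to whatever is collected before the dose.

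**2. Size for ALT (illustration)**

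The plan gives no figure to reproduce, and 4.6.3.2 sets no threshold. I used 3 × ULN because the protocol's liver criteria (Appendix F) use it.

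*From the documents:* SD of change in log ALT 0.50 and a 25% decrease at end of treatment (Protocol 9.2, SAP 1.3); screening ALT above 1 and up to 5 × ULN; post-dose values at Weeks 2, 4, 8 and 12; 45 per arm.

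*Assumed:* median ALT 1.3, 1.5 or 2.0 × ULN; between-person log-SD 0.3 or 0.5; the correlation over time; and a fall that is log-linear to Week 12.

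Three structures give an SD of change of 0.50 at Week 12:
- A, independent within-person variation: SD = 0.50/√2 = 0.354.
- B, serially correlated variation: correlation 0.9 per week.
- C, within-person SD 0.20, the rest being individual response that grows to Week 12: response SD = √(0.50² − 2 × 0.20²) = √0.17 = 0.41.

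Quantity simulated (600,000 profiles per setting before the screening filter): P(Day 1 ≥ 3 × ULN and all four post-dose values < 3 × ULN).

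| Structure | Stable ALT | Gradual 25% fall |
|---|---|---|
| A | 2.5–5.1% | 3.3–8.0% |
| B | 1.9–3.2% | 2.7–5.2% |
| C | 0.6–3.1% | 0.8–5.0% |

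Per 45 participants, stable ALT gives 0.006 × 45 = 0.3 to 0.051 × 45 = 2.3. The gradual fall gives 0.008 × 45 = 0.4 to 0.080 × 45 = 3.6.

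**3. Effect on the comparison of arms**

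Take stable placebo against a gradual 25% fall on active treatment. Under A and B the difference in the share displayed at ≥ 3 × ULN is 6.4–14.1 points from post-dose values alone and 5.6–11.2 points with Day 1 included. Setting by setting, the loss equals the pre-dose-only share on active minus that on placebo. It is 0.7–3.0 points under A, within that range under B, and 0.2–2.0 points under C. Overall it is 0.2–3.0 points, or roughly 0.1 to 1.3 participants per 45.

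**4. Can it hide harm?**

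No. Adding a value to a set cannot lower its maximum. Under A and B, with a true 1.5-fold rise already present at Week 2, the pre-dose-only share is below 1%.

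AST, bilirubin and urinalysis were not simulated.

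**The case against.** The best defence is that the SAP plainly treats baseline and on-treatment values as different things. Appendix 7.1 assigns the sample to baseline. The ECG section (4.6.7.2) asks for a post-baseline value on treatment. The sentence on maxima directly follows one limited to assessments after baseline. The amendment history also shows the intent, referring to "measurements done prior to first dose on first dose day. These are to be in the pre-treatment period". A sensible programmer might therefore exclude the sample. That makes the right result likely but does not secure it: the operative definition is by date, and the ECG section states the very limit that these displays lack. The amendment history is evidence of intent only. A reader might treat its difference from the body text as an error in itself; it is not one, and the point does not rest on it.

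The objections on size largely stand. The numbers depend on assumptions, and attributing part of the 0.50 SD to individual response lowers them (structure C). What shrinks is an apparent benefit in a descriptive output, while ALT benefit is tested by the primary endpoint. The by-visit summaries and shift tables in 4.6.3.2 give further views of the same data.

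A reader might infer that liver-safety monitoring is compromised. The documents do not support that. Hy's Law cases are identified by investigator review of laboratory reports (Protocol Appendix F 3). The ALT/bilirubin quadrant is little affected, because bilirubin above ULN is excluded at entry except in known Gilbert's disease. Conversely, a reader might take the problem to be confined to one display; the wording of 4.6.4.1 shows that it is not.

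**Conclusion.** Wrong as written, and minor. The SAP's own definitions place pre-dose Day 1 laboratory values inside both safety periods, and neither 4.6.3.2 nor 4.6.4.1 takes them out. This conclusion comes from the text and needs no simulation.

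The size is illustrative only. About 0.6–5% of participants with stable ALT, or 0.8–8% with a gradual 25% fall, would be shown at or above 3 × ULN solely from the pre-dose sample. The loss in the between-arm difference is about 0.2–3 percentage points. Median ALT, between-person SD, correlation and time course are assumed, and the threshold is not the SAP's.

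The effect is confined to descriptive safety displays. Post-dose rises remain visible, and neither Hy's Law identification nor the primary analysis changes.

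**What to change.** In SAP 3.3.1.2, or in both 4.6.3.2 and 4.6.4.1, state for laboratory data:
- Only values collected after the date and time of first dose count as on-treatment or on-study.
- If a time is missing, the Day 1 value chosen as baseline under Appendix 7.1 counts as pre-treatment.
- Any Day 1 value known to be post-dose stays in the maximum or minimum, even if it serves as baseline under the third bullet of 7.1.

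The last line is why simply inserting the term post-baseline is not enough. Under that third bullet, the first value on or after dosing becomes baseline when no earlier Day 1 value qualifies, so the shorter wording would drop a genuine post-dose value.

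The cost is a few words of SAP text and a small programming change. No new data are needed: Protocol 6.4 already provides for recording the date and, where applicable, the time of clinic doses, and the missing-time rule covers gaps.
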